6.11.2. Schedule of Activities: After 52 Weeks of Study Treatment

For subjects who, for any COVID-19-related reason, cannot perform study procedures, the possibility to conduct phone/televisits and home (or other remote location) visits, and alternative assessment procedures are detailed in Section 6.1.1.

EVENT	AFTER 52 WEEKS OF STUDY TREATMENT				
	Every 12 weeks up to EoST/EoSA ±7 d	Every 24 weeks up to EoST/EoSA3 ±7 d	ETD	EoST/EoSA*	FU* (4 weeks after EoST/EoSA) ±7 d
Study visit					
Study weeks ± visit window					
Alcohol consumption and smoking habits (Section 6.3)	✓		✓	✓	
Physical examination (Section 6.6.3)	✓		✓	✓	
Vital signs (Section 6.6.4)	✓		✓	✓	
ECG single recording (Section 6.6.5)			✓	✓	
ECG single recording before IMP intake (Section 6.6.5)	✓				
Pregnancy test (urine) (Sections 6.6.2 and 4.5.3.1.1)	✓		✓	✓	
Clinical laboratory tests (Section 6.6.2)	✓		✓	✓	
Spirometry (Section 6.5.1.1)	✓		✓	✓	
DLCO (Section 6.5.1.2)		✓			
██████████ (Section 6.5.1.3)	✓		✓	✓	
6MWT ██████████ (Section 6.5.4)		✓			
Dispense IMP (Section 5.2)	✓				
Collect IMP/perform drug accountability (Section 5.5)	✓		✓	✓	

EVENT	AFTER 52 WEEKS OF STUDY TREATMENT				
	Every 12 weeks up to EoST/EoSA ±7 d	Every 24 weeks up to EoST/EoSA3 ±7 d	ETD	EoST/EoSA*	FU* (4 weeks after EoST/EoSA) ±7 d
Study visit					
Study weeks ± visit window					
Diary card dispensing and collection (as applicable per visit) for drug accountability (Sections 5.5 and 6.4)	✓		✓	✓	
EQ-5D and SGRQ (ePRO) (Section 6.5.3)		✓	✓	✓	
LCQ and K-BILD questionnaire (ePRO) (Section 6.5.3)		✓	✓	✓	
VAS Cough and Urge to Cough (Section 6.5.3)		✓	✓	✓	
PK blood samples (Section 6.7)			✓	✓	
PK blood samples before IMP, but 2-6 hours after N intake (Section 6.7)1	✓				
PK blood samples before IMP, but after P or N intake (Section 6.7)2		✓			
██████████ (Section 6.8)			✓	✓	✓
██████████ (Section 6.8)		✓			
██████████ (Section 6.9.1)			✓	✓	
██████████ (Section 6.9.1) ██████████		✓			
Vital status (Section 4.5.4)				✓	✓
Study medication intake (Section 5.2)	Throughout the treatment period				
AE assessment (Section 6.6.1)	Throughout the study				

EVENT	AFTER 52 WEEKS OF STUDY TREATMENT				
	Every 12 weeks up to EoST/EoSA ± 7 d	Every 24 weeks up to EoST/EoSA3 ± 7 d	ETD	EoST/EoSA*	FU*
Study visit					
Study weeks \pm visit window					(4 weeks after EoST/EoSA) ± 7 d
Concomitant medication assessment and documentation (Section 4.5.3.2)	Throughout the study				

d=days, ETD=early treatment discontinuation (i.e. before the EoST/EoSA visit), ePRO=electronic patient-reported outcome, EoST/EoSA=end of study treatment/end of study assessments, N=nintedanib, P=pirfenidone.

The preferred sequence of study assessments is described in Section 6.1.

¹ Only for subjects taking nintedanib at screening and randomization, until they stop taking nintedanib

² For subjects not taking nintedanib at screening and randomization and those stopping nintedanib during the study

³ At these visits, the assessments from both the Every 12 weeks up to EoST/EoSA and the Every 24 weeks up to EoST/EoSA columns are included

* This can be a scheduled clinical study center visit or a phone call.

7. STATISTICAL METHODS

All statistical methods shall be detailed in the statistical analysis plan (SAP) that will be finalized prior to the database lock and unblinding. Data collected in this clinical study will be documented using summary tables, figures, and subject data listings, as appropriate.

All statistical analyses will be performed by the CRO using the SAS (Version 9.1.3 or higher) software for statistical computations and SAS or R Studio for graphical purposes.

Any deviations from the statistical analyses planned in this protocol will be documented in the SAP.

A protocol deviations plan will include the definition of major and minor protocol deviations and the identification of major protocol deviations which will be excluded from the per-protocol analysis. The assessments of protocol deviations (major/minor) will be done prior to database lock and unblinding.

7.1. Determination of Sample Size

To account for multiple testing due to multiple doses, a Bonferroni approach [9] will be applied to the alpha level with higher priority given to the high-dose group. The primary endpoint will be tested at a 4% level when comparing GLPG1690 600 mg to placebo and a 1% level for GLPG1690 200 mg group versus placebo.

Denoting Δ_{600} and Δ_{200} , the true treatment differences of the two GLPG1690 treatment groups with placebo, and assuming a common standard deviation (SD) on the 52 weeks decline in FVC of 275 mL, the probabilities that 0, 1, or 2 treatment comparisons with placebo are statistically significant, are presented in Table 2. The family-wise error rate is protected at 5% using the Bonferroni procedure. The so-called disjuncture power of the study is the probability that 1 or 2 hypotheses are rejected and is displayed in the right-most column of Table 2.

A meta-analysis of the seven placebo-controlled studies that have been conducted on nintedanib, pirfenidone, and pamrevlumab has revealed that the treatment effect at 52 weeks is estimated to be approximately 119 mL in a treatment-naïve population, the effect observed with nintedanib alone is similar (112 mL) [32]. Little information is available on the expected treatment effect of GLPG1690 in addition to pirfenidone or nintedanib. Table 2 gives an overview of the power for different scenarios for the overall treatment effect in the population of subjects on standard of care (either pirfenidone or nintedanib, or neither pirfenidone nor nintedanib).

Since the linear-slope model on the annual rate of decline in FVC accounts for missing data, the number of subjects randomized and the number of subjects included in the model is expected to be equal. An equal number of 250 subjects will be randomized to each treatment group to have at least 80% power to show a significant effect assuming the 600-mg group has a treatment effect of at least 80 mL in the overall population of treatment naïve and patients on standard of care.

Table 2: Probability of Statistical Significance of 0, 1, or 2 Treatment Comparisons With Placebo

mL	0 Successful	1 Successful	2 Successful	Power
$\Delta_{600}=80$ $\Delta_{200}=80$	6.8%	23.4%	69.9%	93.2%
$\Delta_{600}=80$ $\Delta_{200}=60$	10.1%	46.9%	43.0%	89.9%
$\Delta_{600}=80$ $\Delta_{200}=20$	11.5%	84.4%	4.1%	88.5%
$\Delta_{600}=80$ $\Delta_{200}=0$	11.2%	88.0%	0.7%	88.8%
$\Delta_{600}=90$ $\Delta_{200}=60$	5.1%	51.1%	43.8%	94.9%
$\Delta_{600}=50$ $\Delta_{200}=50$	43.9%	34.3%	21.9%	56.1%
$\Delta_{600}=50$ $\Delta_{200}=0$	50.6%	48.9%	0.5%	49.4%
$\Delta_{600}=0$ $\Delta_{200}=0$	95.2%	4.5%	0.3%	4.8%

Based on a review of the blinded data, the SD may be reassessed.

7.2. Populations for Analyses

7.2.1. All Screened Subjects

All enrolled subjects who underwent screening assessments to check whether or not they are eligible to participate in the clinical study.

7.2.2. All Randomized Subjects

All enrolled subjects who underwent all screening assessments and were found to be eligible for the clinical study and who were randomized into the clinical study.

7.2.3. Full Analysis Set

All randomized subjects who received at least one dose of IMP.

7.2.4. Per-Protocol Set

All randomized subjects who received at least one dose of IMP, excluding subjects/data points with a major protocol violation which impacts the efficacy results.

7.2.5. Pharmacokinetic Analysis Set

All randomized subjects who received at least one dose of IMP and for whom evaluable PK data were available (e.g. excluding all protocol violations/deviations or AEs that may have an impact on the PK analysis).

7.2.6. [REDACTED]**7.3. Statistical Analyses****7.3.1. General Statistical Considerations**

Summary tabulations will be presented and will display the number of observations, mean, SD or standard error, as appropriate, median, minimum, and maximum for continuous variables, and the number and percentage per category for categorical data. In addition to tabulated descriptive statistics, graphical data displays may be used to summarize the data. Unless otherwise noted, inferential statistics will be interpreted at the two-sided 5% level.

7.3.2. Interim Analysis

An IDMC will review the data of this study and the identically designed GLPG1690-CL-303 study on a regular basis. An interim analysis to assess futility will be performed when a reasonable number of subjects have completed 52 weeks of treatment (e.g. at least 25% subjects from the two studies combined). No interim analysis for early termination for efficacy will be performed and therefore no adjustment of the alpha level is necessary. Details on the IDMC are given in Section 8.1 and in the charter.

7.3.3. Analyses of Demographics and Baseline Characteristics

Summary statistics (mean, median, SD, minimum, maximum, number of available observations) will be provided by treatment group for continuous demographic variables (e.g. age, height, weight). Categorical endpoints will be presented by number and percentage of subjects per category. Results will be presented for the full analysis set (FAS).

Subject disposition (including reasons for early discontinuation), protocol deviations, demographics, baseline characteristics, medical history, prior and concomitant therapies, and use of IMP will be analyzed descriptively by treatment group and/or listed. No statistical inference will be performed.

Medical history terms will be coded using Medical Dictionary for Regulatory Activities (MedDRA) and presented by the number of subjects with at least one event by System Organ Class, Preferred Term, and treatment group.

[figure not shown]
Prior and concomitant medications will be coded by the sponsor according to the World Health Organization (WHO) drug code and the Anatomical Therapeutic Classification (ATC) class code and tabulated by the number and percentages of subjects with a medication per ATC code and treatment group.

7.3.4. Analyses of Efficacy Parameters**Multiplicity Adjustment**

To account for the multiple testing due to two doses being compared to placebo, a Bonferroni approach [9] will be used with higher priority given to the high-dose group. The primary

endpoint will be tested at a 4% level when comparing GLPG1690 600 mg to placebo and a 1% level for GLPG1690 200 mg group versus placebo.

With respect to the multiplicity adjustment for the key secondary endpoints an additional approach was requested by [REDACTED] compared to EU countries. For countries outside US and EU, the EU approach will be applied.

For Countries outside the US:

To increase the probability to detect a potential treatment effect on the key secondary endpoints, some of which are rare but clinically important events, they will be analyzed using the pooled data from the two studies (GLPG1690-CL-303 and GLPG1690-CL-304). The confirmatory testing on these secondary endpoints will be done only if the primary endpoints in both studies show significance and a step-down closed-testing multiplicity adjustment will be applied, as shown in [Figure 4](#). A key secondary endpoint in the pooled analysis will only be tested for a dose if the higher order endpoint also showed significant for that dose. Details of the pooled analyses will be provided in the pooled-analysis SAP.

Results for the key secondary endpoints for each individual study will enable the evaluation of consistency of the results between the studies. An overview of the multiplicity adjustment for the primary and key secondary endpoints is provided in [Figure 4](#).

[figure not shown]

Figure 4 Multiplicity adjustment within study approach

No interim analysis for early termination for efficacy will be performed and therefore, no adjustment of the alpha level is needed.

Efficacy Analyses

All efficacy parameters (e.g. spirometry, clinical endpoints, quality of life) will be analyzed descriptively and FVC and %FVC will also be analyzed for a series of subgroups (such as baseline characteristics, background treatment, and stratum). The primary analyses will be conducted on the FAS population.

Spirometry Data

- The primary time point will be Week 52. Analyses at the end of the study are secondary.
- The rate of decline in FVC will be analyzed using a random coefficient regression model (linear slope model) including sex, age, height, and stratification factor as covariates and a random intercept and slope. The treatment effect is determined by using estimated average slopes for each treatment group on the basis of the treatment*time interaction term from the above mixed model, with time as a continuous factor and treatment as a categorical factor. All available FVC values from baseline to Week 52 will primarily be used, including those from the ETD visit for subjects who discontinued early and do not complete their study visits up to Week 52.
- As a secondary analysis, the same model will be fit using all data until the end of the study.
- The proportion of subjects who have an absolute decline $\geq 10\%$ in %FVC at least once during the study or who die will be analyzed using logistic regression including sex, age, height, and stratum as factors using data up to Week 52.
- In addition, the same will be presented using all data up to the end of the study. A time-to-event analysis may also be used to analyze the composite endpoint of %FVC decline and mortality up to the end of the study.
- The %FVC change from baseline will be analyzed using a similar random coefficient regression model (linear slope model) as FVC in mL.

- Other spirometry endpoints will be summarized descriptively, similar to FVC.

Sensitivity analyses including multiple imputation methods and a per-protocol analysis will be performed to assess the impact of missing data, noncompliance, and protocol violations on the primary efficacy analyses. Additional exploratory analyses and graphical presentations may be performed when deemed useful to better understand the data. Details will be described in the SAP.

Time-to-event Data (Including Hospitalization, First Acute IPF Exacerbation, Mortality, and [Qualifying for] Lung Transplant), Using All Data up to the End of the Study

- Time-to-event endpoints will be graphically presented by Kaplan-Meier estimates. In addition, a Cox proportional-hazards model with terms for age, sex, height, and stratum will be used to analyze the hazard ratios for each dose compared to placebo.

Other Efficacy Endpoints

- A mixed-effects model with treatment, time (as a categorical factor), treatment*time, and baseline total score as factors in the model will be applied to the change from baseline in SGRQ total score.
- The change from baseline in DLCO will be analyzed similarly as change in SGRQ.
- EQ-5D, SGRQ total score and domains, LCQ total score and domains, K-BILD total score and domains, and VAS Cough and Urge to Cough will be presented using descriptive statistics by treatment group of actual values and changes from baseline at all time points. The proportion of SGRQ responders (defined as absolute change from baseline at all time points in SGRQ total score ≤ -4 points) will also be tabulated by treatment group.
- The proportion of SGRQ responders and the proportion of subjects with hospitalization will be analyzed using a logistic regression model similarly as described above and presented by treatment group.
- The actual values and changes from baseline of 6MWT [REDACTED] will be presented descriptively for each time point by treatment group.

[REDACTED]

More details will be described in the SAP.

7.3.5. Analyses of Safety Data

The safety analysis will be conducted on the FAS population.

All safety data collected on or after the first dose of IMP intake up to the last follow-up visit after the last dose will be summarized by treatment group. Clinical safety will be addressed by assessing AEs, laboratory assessments, physical examinations, vital signs, and 12-lead ECGs. More details will be described in the SAP.

7.3.5.1. Extent of Exposure

A subject's extent of exposure to IMP will be generated from the IMP administration page of the CRF. Exposure data will be summarized by treatment group. Duration of exposure to IMP will be expressed as the number of weeks between the first and last dose of IMP, inclusive, regardless of temporary interruptions in IMP administration and summarized by treatment group. Results will be presented for the 52-week and for the complete study period, separately.

7.3.5.2. Adverse Events

Clinical and laboratory AEs will be coded using the latest version of the Medical Dictionary for Regulatory Activities. System Organ Class, High-Level Group Term, High-Level Term, Preferred Term, and Lower-Level Term will be attached to the clinical database.

The following AEs will be considered as TEAEs:

Any AE with an onset date on or after the start of IMP intake and no later than 30 days after last dose of IMP, or any worsening of any AE on or after the start of IMP intake.

Selected tables will also be presented including all AEs which occurred after the start of IMP intake up to the end of the study.

Summaries (number and percentage of subjects) of TEAEs by System Organ Class and Preferred Term will be provided by treatment group. TEAEs will also be summarized by causal relationship to IMP and severity. In addition, TEAEs leading to premature discontinuation of IMP will be summarized and listed. Also, all SAEs, including the non-treatment-emergent SAEs, will be listed.

7.3.5.3. Clinical Laboratory Evaluations

Laboratory assessments will be analyzed descriptively. Changes from baseline (Day 1 before IMP intake) and shifts according to normal ranges will be presented as well. Analyses will be done per treatment group.

7.3.5.4. Physical Examinations

Physical examination results will be summarized by body system and treatment group.

7.3.5.5. Vital Signs

Vital signs will be analyzed descriptively. Changes from baseline (Day 1 before IMP intake) and shifts according to normal ranges will be presented as well. Analyses will be done per treatment group.

7.3.5.6. Electrocardiogram

ECG will be analyzed descriptively. Changes from baseline (Day 1 before IMP intake) and shifts according to normal ranges will be presented as well. Frequency analyses of subjects with a QTc or QTcF prolongation of >500 ms and with a QTc or QTcF increase >60 ms change from baseline will be presented as well. Analyses will be done per treatment group.

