At Visit 3 (after IMP intake) and Visit 4 (before and after IMP intake), abnormal triplicate ECGs and their confirmatory repeat reading will be transmitted to the central reader for expedited review. Refer to Section 4.5.4 for details on abnormal ECG readings.

For other time points with abnormal ECG reading, the investigator should alert the central reader. In that case, the ECG will be reviewed as soon as possible on the same day. The conclusion/evaluation of the central cardiologist reader will overrule the reading of the ECG device.

At other time points with normal ECG reading, the standard review times will be adhered to.

In case an indwelling catheter is used, ECGs may be recorded after blood sampling, provided that there is at least 30 minutes between catheter insertion and the ECG recording. When

catheter insertion would fail, the ECG needs to be taken before the venipuncture and at least 30 minutes after the failed attempt.

ECG parameters to be recorded include the following: heart rate, PR interval, QRS interval, uncorrected QT interval, QTc, morphology, and rhythm. QTcF will be considered as normal if ≤ 450 ms. A prolongation of QTcF to >500 ms or an increase from baseline of >60 ms will be considered a threshold of concern and the subject should be discontinued (for details, refer to Section 4.5.4). Normal ranges for ECG are provided in Appendix 8.

ECG abnormalities will be interpreted by the investigator for clinical significance. Clinically significant abnormal values should be recorded as AEs.

If subjects, due to any COVID-19-related reason, cannot attend visits on site, see Section 6.1.1.

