APPENDIX 8: NORMAL RANGES FOR VITAL SIGNS, [REDACTED] [REDACTED] AND ECG PARAMETERS

NORMAL RANGES FOR VITAL SIGNS

Normal ranges applicable in supine position (after at least 5 minutes):

SBP (mmHg)	DBP (mmHg)	Heart rate (bpm)	Body temperature (°C)	Respiratory rate (RR) (breaths/minute)
$90 \leq \text{SBP} \leq 150$	$45 \leq \text{DBP} \leq 90$	$50 \leq \text{HR} \leq 100$	$35.5 \leq t \leq 37.5$	$12 \leq \text{RR} \leq 18$

bpm = beats per minute

NORMAL RANGES FOR ECG PARAMETERS

Normal ranges applicable in supine position (after 5 minutes):

PR (ms)	QRS (ms)	QTcF (ms)	Heart rate (bpm)
$120 \leq \text{PR} \leq 220$	$\text{QRS} \leq 120$	$\text{QTcF} \leq 450$	$50 \leq \text{HR} \leq 100$

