	9.3.6.3 VAS Cough and Urge to Cough
9.3.7	Functional Exercise Capacity and it is all analyses omitted, except for total distance walked in 6 minutes, this parameter will be analyzed.
9.3.9	- No subject profiles will be created.
9.3.10	No analyses per age, sex, race and per geographical region will be done.
9.3.11	
9.4.5	Physical examinations frequency table
9.4.3.6	
 
Tabulation of ECG interpretations
 
Table summarizing the pre- and postdose values at these selected visits.
 

Tables and listings to investigate the impact of COVID-19 on the study have been added.

If changes are needed after unblinding, these will be documented in the CSR with an explanation for the reason for the change.

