#### 9.4.3.3. Normal Ranges

For the QT and QTcF parameters, the following categorizations will be used:

- of the actual values:
  - <= 450 ms,
  - >450 ≤480 ms,
  - >480- ≤500 ms,
  - >500 ms;
- of the changes from baseline:
  - <= 30 ms (including all decreases in QT),
  - >30- ≤60 ms,
  - >60 ms.

For PR interval, the following categorizations will be done:

- Low: < 120 ms,
- Normal:  $\geq 120 \leq 220 \text{ ms}$ ,
- High: >220 ms;

For heart rate, the following categorizations will be done:

• Low: < 50 bpm,
- Normal:  $\geq 50 \leq 100$  bpm,
- High: >100 bpm;

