### 9.4.3.6. Analyses

No formal inferential statistics (p-values) will be derived.

Descriptive statistics will be summarized of the actual values and change from baseline (including 95% CI of the mean change) per parameter and unit, treatment group and time point. The actual value at baseline will also be presented in this table. Only pre-dose assessments will be used for this table. A similar summary table as for labs will also be provided.

In addition to the predose measurements, ECGs are also taken 2-3 hours postdose on selected visits (Day 1, Week 2, 4, 12 and 34 for ECG). These postdose measurements will not be taken into account in the windowing for the above tables, but an additional table will be created summarizing the pre- and postdose values at these selected visits.

All ECG abnormalities after the first dose of IP up to 30 days after the last dose will be included for consistency with AE reporting.

Abnormalities of the actual values will be presented as shift tables of the worst-case abnormality versus the baseline abnormality. The table will be created per parameter (QT, QTcF, PR and heart rate), treatment group and analysis period.

A frequency table of the number (percent) of subjects with treatment-emergent worst-case abnormalities and the worst change per parameter (QT, QTcF, PR and heart rate), treatment group and analysis period will be presented.

Frequency table per treatment group and time point of the ECG interpretation scores as recorded in the eCRF. Note that more than one of these items can be ticked.

No figures are planned for ECGs.

Listing will be provided per treatment group, per subject and per time point of all postbaseline data scored as out-of-normal-range or postbaseline clinically significant, plus also the baseline reference time point.

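### The protocol promises ECG shifts against normal ranges and gives a range for QRS, but the SAP leaves QRS out of every category, shift and frequency table without recording the departure

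*Protocol*

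**What the plan says.** Protocol section 6.6.5 sets out what is captured: "ECG parameters to be recorded include the following: heart rate, PR interval, QRS interval, uncorrected QT interval, QTc, morphology, and rhythm". It refers to Appendix 8 for the normal ranges. Under the title "NORMAL RANGES FOR ECG PARAMETERS", that appendix lists PR from 120 to 220 ms, QRS up to 120 ms, QTcF up to 450 ms and heart rate from 50 to 100 bpm. It gives no range for uncorrected QT.

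Protocol section 7.3.5.6 commits to the analysis: "ECG will be analyzed descriptively. Changes from baseline (Day 1 before IMP intake) and shifts according to normal ranges will be presented as well". It requires this per treatment group and excludes no parameter. It separately asks for counts of QTc or QTcF above 500 ms and of increases above 60 ms.

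SAP section 9.4.3.3 begins "For the QT and QTcF parameters, the following categorizations will be used" and then adds categories for PR and heart rate. Sections 9.4.3.4 and 9.4.3.5 derive worst-case values for the same four parameters. On the shift table, section 9.4.3.6 says: "The table will be created per parameter (QT, QTcF, PR and heart rate), treatment group and analysis period". The treatment-emergent frequency table carries the same list.

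Protocol section 7 also sets a rule for departures: "Any deviations from the statistical analyses planned in this protocol will be documented in the SAP".

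**The concern.** The two documents disagree about a safety output. The protocol promises range shifts for the ECG and names a range for QRS. The SAP, followed as written, produces none for QRS. The list of changes in SAP section 9.1 does not mention it, so a reader of the study report would have no sign that a promised table is missing.

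The protocol treats conduction as a safety matter. Clinically significant conduction abnormalities on the ECG are an exclusion criterion (section 4.5.2, criterion 8.1), and a conduction abnormality of CTCAE Grade 3 or higher is a reason to stop study drug (section 4.5.4). At stake is the by-arm count of subjects whose measured QRS crosses the protocol's own limit, independent of whether an investigator judged the tracing clinically significant.

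**Working it through.** The plan states no figure for this point, so the check is one of coverage.

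**Step 1. Parameter by parameter.**

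| Parameter | Appendix 8 range | SAP category (9.4.3.3) | Worst-case rule (9.4.3.4–9.4.3.5) | Shift and frequency tables (9.4.3.6) |
|---|---|---|---|---|
| PR | yes | yes | yes | yes |
| QRS | yes (up to 120 ms) | no | no | no |
| QTcF | yes | yes | yes | yes |
| Heart rate | yes | yes | yes | yes |
| Uncorrected QT | none | yes | yes | yes |

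Three of the four Appendix 8 parameters carry through. QRS does not.

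**Step 2. Is this specific to the ECG?** Protocol section 7.3.5.5 makes the same promise of shifts for vital signs. There, SAP section 9.4.4.1 adopts the Appendix 8 ranges by reference.

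**Step 3. Is it declared?** SAP section 9.1 keeps safety endpoints in scope for the abbreviated report and itemises what is dropped. For section 9.4.3.6 it lists two items: "Tabulation of ECG interpretations" and the table of pre- and postdose values. QRS is not listed.

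**Step 4. Do other outputs give the missing count?**
- *Descriptive statistics.* These run per parameter and do not exclude QRS. SAP section 7.1 includes the SD, median, minimum and maximum. A maximum shows that an extreme value exists, not how many subjects in an arm exceeded 120 ms. This table uses predose readings only, whereas the worst-case rules use all postbaseline records.
- *Listing.* It covers postbaseline data scored as out of range or flagged clinically significant. QRS has no scoring rule, so it is unclear whether an unflagged value above 120 ms would appear. A listing is in any case not a count.
- *Adverse event tables.* Protocol section 6.6.5 requires clinically significant ECG abnormalities to be recorded as adverse events. Section 9.1.5 covers those that need intervention, come with symptoms or change study drug. SAP section 9.4.1.6 counts these by arm. Values not reported as adverse events are left out.

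**Step 5. Why a mean does not replace a count (illustration on assumed inputs).** Take 250 subjects per arm (protocol section 7.1). Assume that 4% of an active arm widen by 30 ms and that the SD of change is 8 to 10 ms. None of these three values is in the documents.
- Subjects affected: 0.04 × 250 = 10.
- Shift in the arm mean: 0.04 × 30 = 1.2 ms.
- Standard error of the difference: SD × √(2/250) = 0.72 to 0.89 ms.
- Ratio: 1.2/0.89 to 1.2/0.72, about 1.3 to 1.7 standard errors.

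All 10 would cross 120 ms only if each started above 90 ms, so the category count could be lower.

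**The case against.** The strongest reply is that little is lost. PR is itself a conduction interval and is fully categorised and tabulated by arm. A conduction event that stops study drug appears in the by-arm table of adverse events leading to discontinuation. The dropping of the ECG interpretation table is declared in SAP section 9.1. Safety pharmacology found no biologically relevant cardiovascular effect (protocol section 2.1.2.2), the QT prolongation in dogs was judged non-adverse (section 2.1.4.1), and no stopping rule is specific to QRS. The studies have been halted and no marketing application will follow. All of this stands and limits the weight of the point. It does not supply the missing table or the missing declaration.

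Three stronger readings might be inferred, and the documents do not support them:
- *That conduction harm is never counted by arm.* PR shifts and conduction adverse events are counted.
- *That QRS can show only in a mean.* The descriptive statistics also give the spread and the extremes, and the listing may show flagged values.
- *That uncorrected QT was graded in place of QRS.* QT is graded alongside QTcF, and nothing says that it replaces QRS.

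Grading uncorrected QT with corrected-QT limits is hard to interpret, because QT varies with heart rate. With the cube-root correction (SAP section 9.4.3.1), QT = QTcF × (60/HR)^(1/3). The 450 ms limit on QT then corresponds to a QTcF of 450/1.0627 = 423.5 ms at 50 bpm and 450/0.8434 = 533.5 ms at 100 bpm. But QTcF keeps all its own categories, so no promised QT analysis is lost.

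**Conclusion.** The protocol and the SAP contradict each other on one safety parameter. QRS has a protocol normal range and falls under the promise of shifts by arm, yet the SAP gives it no category, worst-case rule, shift table or frequency table, and does not record the departure. The affected output is one of four Appendix 8 ECG parameters. What goes uncounted by arm is QRS above 120 ms that was not reported as an adverse event.

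This rests on the text alone and needs no numerical assumption. The number of subjects concerned cannot be derived from the documents, and the illustration above should not be read as an estimate of it. The point is small but worth correcting, because it restores a promised safety table on data that the protocol already collects.

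**What to change.** 1. In SAP section 9.4.3.3, add QRS with the Appendix 8 limit: normal up to 120 ms, high above 120 ms. There is no low category.
2. Add QRS to the worst-case rule in section 9.4.3.5 and to the parameter lists of the shift and treatment-emergent frequency tables in section 9.4.3.6. Scoring QRS also settles whether out-of-range values reach the listing.
3. If QRS is to stay out, record that in section 9.1 as a departure from protocol section 7.3.5.6, with the reason.

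Removing the categories for uncorrected QT is optional, since QTcF is fully tabulated.

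The cost is a few lines of SAP text and one more parameter in tables already specified. No new data collection is needed, since QRS is among the parameters recorded under protocol section 6.6.5.
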